# 8.2.2. Product Preparation

Before use, all vials must be inspected visually for discoloration, particles and fibers; if the contents of a vial is cloudy or contain particulate material, the vial must not be used. Subgam-VF is to be infused at room temperature (vial not cold when touched).

Page 35 of 87

#### 8.2.3. Method of Administration

Subgam-VF should only be infused subcutaneously using an infusion pump. Subgam-VF can be infused into the following sites: abdomen, thigh, upper arm and/or lateral hip.

The dose of Subgam-VF can be given into multiple infusion sites (although this should be no more than six sites, and eight sites for subjects  $\geq 100 \text{ kg}$ ). If more sites are needed to achieve a full dose, then the sites can be used consecutively, but the infusions should be at least two inches apart.

Only one batch of Subgam-VF should be infused during any one infusion session.

Subgam-VF infusions will be administered in accordance with the table below, the maximum volumes and flow rates may be reduced according to tolerability.

Table 1 – Recommended infusion flow rates for Subgam-VF

	Volume	Rate
First infusion	20 mL/site	20 mL/hr/site
Maximum at	Up to 30 mL/site	Up to 30 mL/hr/site
subsequent infusions		

- Up to six infusion sites can be used simultaneously. Subjects weighing ≥100 kg may use up to eight sites if necessary. If more sites are required, these must be used consecutively (during the same infusion).
- Any increase in flow rate or number of sites should first be tried whilst the subject is in the clinic. However, the infusions must be administered at the volume and rate outlined in Table 1 throughout the entire infusion. **Titration during the infusion is not allowed.**
- For young children or adults of below average weight lower flow rates may be used, depending on tolerability.

Details on how to prepare and administer the Subgam-VF infusion can be found in the Patient Medication Guide.

Full training must be provided to the subject prior to self-administration at home or other appropriate setting. It is aimed to start home-therapy at Week 3, however if the subject requires further training this will be provided (i.e. it is not mandatory that the infusions are performed at home from Week 3).

Lack of tolerance at any given rate must be recorded as an AE at that rate. If a subject has had the same treatment related AE at the same rate twice, and those AEs have been recorded, then subsequent infusion rate should be halted at the previously highest tolerated rate.

Page 36 of 87

If any AE(s) occur, these will be documented as detailed in section 10.3. The infusion may then be resumed at a rate tolerated by the subject.

# 8.2.4. Product Accountability

The Investigator is responsible for the accountability of all used and unused product utilized in the study. Product accountability must be maintained as detailed in the Pharmacy Manual.

An IP accountability log for Subgam-VF must be kept current by the site.

The Pharmacy Manual will contain further information on IP accountability during the study, including disposal.

Subgam-VF must not be used outside of this protocol and must not be used for subjects who are not in this study.

# 8.3. Treatment Compliance

Subgam-VF will be administered subcutaneously both at the study site and also by self-administration at home. Subjects will be required to keep diaries and records of Subgam-VF usage. Site staff will check at each study site visit that the product is being stored appropriately, administered correctly and safely and the correct volume infused.

## 9. ASSESSMENT OF EFFICACY

## 9.1. Primary Efficacy Variables

As this is a pharmacokinetic and safety study, no formal efficacy analyses are planned.

# 10. ASSESSMENT OF SAFETY AND TOLERABILITY

# 10.1. Safety Variables

Safety endpoints include assessment of adverse events and adverse drug reactions, significant changes in vital signs, safety laboratory parameters (including kidney and liver function and Direct Coombs' test), virology, physical examination or medical history during the study.

The variables used to assess safety will be the following:

- Adverse Events
  - The number and percent of adverse events (AEs) including infusion site reactions.
  - The number and percent of infusions associated with one or more AEs that begin during the infusion, up to one hour, 24 hours, 48 hours or within 72 hours after completion of the infusion.
  - An adverse reaction will be defined as any TEAE (irrespective of causality) that occurs during the infusion or within 72 hours after completion of the infusion, any AE classed as product related or any AE with unknown causality.
  - Thrombotic events
  - Nature, severity, and frequency of AEs (tolerability)
  - Suspected unexpected serious adverse reactions (SUSARs), if any
- Vital signs
- Clinical laboratory tests including tests for hemolysis
- Transmission of viruses
- Physical examination

## 10.2. Adverse Events

• The definitions and procedures for reporting AEs is detailed in Appendix I. AEs will be documented from the date the Informed Consent Form or Assent Form is signed until the follow-up visit and then monitored up to 28 days after the last dose of Subgam-VF is infused. AEs will be reviewed and documented by collecting the diaries at each visit and by direct observation during each infusion. In addition there will be a telephone follow up by an appropriately qualified site staff member on day 3 after each site administered and home administered infusion to check for any adverse reactions including infusion site reactions and remind subjects to document these in their subject study diary. The date of infusion is considered to be Day 0. If Day 3 is to fall on a weekend or public holiday then this telephone follow up call should be performed on the closest working day after Day 3 as possible.

The investigator will attempt to establish a diagnosis of the AE based on signs, symptoms, and/or other clinical information. It is the diagnosis that should be documented as the AE and not the individual symptoms.

An adverse reaction will be defined as any TEAE (irrespective of causality) that occurs during the infusion or within 72 hours after completion of the infusion, any AE classed as product

Page 38 of 87

related or any AE with unknown causality.. Also see the most current Subgam-VF Investigator's Brochure listing common product-related AEs.

# 10.3. Infusion Site Reactions

Infusion site reactions will be assessed during the study site infusion visits by the investigator or delegated study staff, but also rated by the subjects during home infusions and recorded in the subject diaries.

Subjects will inspect infusion sites and record any infusion site reactions (including date and time) into their study diary. Subjects will use the following criteria to grade all infusion site reactions in their study diary:

Mild: no limitation to normal activities

Moderate: some limitation to normal activities

**Severe:** inability to carry out normal activity.

All Infusion site reactions will be recorded in the eCRF. However the Investigator will determine if these should be recorded as AEs. Infusion site reactions will be recorded as AEs when the symptoms/signs lead to infusion stop, require concomitant medication, or have an impact on the general condition of the subject as judged by the Investigator. The Investigator will also use their judgment to record the severity of the AE and may use the subjects diary grading to aid that decision.

## 11. ASSESSMENT OF PHARMACOKINETICS

# 11.1. Pharmacokinetics of Subgam-VF for Total IgG Levels

All subjects will undergo a PK assessment (see Appendix IV, Table 2 and 3 for the sampling time points).

Where possible, samples from Steady State Day 1 (24 hours after the infusion at Week 21 or if delayed, up to Week 25) onwards may be collected at the subject's home by an appropriately qualified member of the study team. Alternatively a Home Health Agency may be utilized to take the PK samples outside of the investigational site. The subject would be required to sign an IRB/EC approved consent form to permit the site to share the subject's details with the agency in order for them to collect the sample.

The following PK variables for total IgG levels will be determined for the PK population:

- AUC $_{(0-\tau)}$  area under the plasma concentration-time curve of the dosing interval.
- $sAUC_{(0-\tau)}$  area under the plasma concentration-time curve of the dosing interval standardized to one week. This will be calculated for the historical data only.

- Cmax maximum concentration in plasma.
- $t_{max}$  time to reach the maximum concentration in plasma.
- CL– systemic clearance.

The timing of the collection of blood samples for PK should be as per Table 2. The scheduling has been selected to ensure achievement of steady state of Subgam-VF.

A variation of <10% is allowed in the timing for samples as follows:

Steady State Day 1 (24 hours)  $\pm$  2 hours,

Steady State Day 2 (48 hours)  $\pm$  4 hours

Steady State Day 3 (72 hours)  $\pm$  6 hours

Steady State Day 5 (120 hours)  $\pm$  8 hours

Steady State Day 7 (168 hours)  $\pm$  12 hours.

All PK parameters will be calculated based on absolute (uncorrected) and baseline-adjusted (i.e. trough-adjusted at steady state) concentrations.

Details of the PK methods will be outlined in a PK Analysis Plan. The PK Analysis Plan will be finalized before database lock.

#### 11.2. Other Pharmacokinetic Parameters

The following PK parameters will be listed and summarized descriptively for the ITT population:

- Trough serum IgG levels (measured before every infusion administered at the study site).
- Trough levels of serum IgG subclasses will be measured prior to certain infusions.
- Levels of specific antibodies (*Haemophilus influenzae* B, *Streptococcus pneumoniae*, *Measles*) will be measured prior to certain infusions. The measles assay is for research purposes only and will not be reported to the investigational site.

## 12. INTERIM ANALYSIS

There is no planned interim analysis for this study, however after sufficient adult PK data has been collected, a review of the blood sampling schedules for children will be performed and the PK sampling will be optimized and reduced if possible.

## 13. STATISTICAL METHODS

Details of the statistical methods will be outlined in the Statistical Analysis Plan. The Statistical Analysis Plan will be finalized before database lock.

# 13.1. Sample Size Determination

This study will enroll up to 50 subjects to ensure 30 evaluable subjects. A sample size of approximately 18 adults (aged 16-75 years) and 12 children (aged between or equal to 2 and 15 years), has been decided as recommended by the FDA guidance for IGIV products. For this study, the children will be enrolled across the age groups of 2 to 5 years, 6 to 11 years, and 12 to 15 years with a minimum of four in each age group. All children who receive at least one infusion of Subgam-VF will be included in the safety analysis. Due to the potential for early withdrawals, PK data may not be available on all 12 children and there may be less than 12 evaluable children in the PK analysis. The total number of subjects (adults plus children) evaluable for PK analysis will be at least 30.

Data will be compared to historical data from previous Gammaplex IGIV studies. All the subjects will undergo a PK assessment.

Assuming no true difference exists in average exposure compared with the historical data, 30 evaluable subjects will give greater than 98% power of concluding equivalence assuming a between-subject coefficient of variation (CV) of 18.2 % (equivalently, a standard deviation of logged data of 0.181). If there is a true difference of 10%, power drops to 86%.

# 13.2. Analysis Population

# 13.2.1. Intent-to-treat (ITT) Population

All subjects who receive at least one infusion of Subgam-VF will be included in the intent-to-treat (ITT) population. The ITT population will be used for all safety analyses, summaries of demography and the following PK parameters: trough serum IgG levels, IgG subclasses and specific antibodies.

## 13.2.2. PK population

The PK population will comprise of subjects in the Subgam PK population and subjects in the Gammaplex PK population as described below.

# 13.2.2.1. Subgam PK population

All subjects in the ITT population who have a pre-dose sample at steady state and at least four post-dose samples at steady state, one of them should be the Steady State Day 7 PK sample. In the case of a subject who provides IgG levels at the PK assessment but does not meet the criteria for inclusion in the Subgam PK population, data will be listed only.

## 13.2.2.2. Gammaplex PK population

All subjects from Gammaplex 5% IGIV PID studies (GMX01 and GMX04) who had an evaluable  $AUC_{0-\tau}$ .

Page 41 of 87

## 13.2.2.3. PK Dose-Adjustment population

The PK Dose-Adjustment population is the subset of the PK population which excludes subjects in the Subgam PK population who had prior treatment with another subcutaneous weekly IgG product. Thus the PK Dose-Adjustment population includes all the Gammaplex PK population and those in the Subgam PK population who had previous treatment with IGIV. This population is analysed to estimate a refined dose adjustment factor.

# 13.3. Efficacy Analyses

As this is a pharmacokinetic and safety study, no formal efficacy analyses are planned.

# 13.4. Safety Analysis

#### 13.4.1. Adverse Events

Summaries of AEs will be based on treatment-emergent AEs (TEAEs), defined as those events with onset date between the first infusion date and 28 days after the last infusion.

The number and percent of infusions associated with one or more AEs (irrespective of causality) that occur during the infusion or within 72 hours after completion of the infusion will be calculated. A 1-sided 95% upper confidence bound for this percent will be derived. If the upper bound is less than 40%, excluding local infusion site reactions, the incidence of infusion-related AEs associated with Subgam-VF will be considered acceptable. In addition, the number and percent of subjects who report any AEs and the number and percent of subjects who report any AEs at least possibly related to Subgam-VF will be calculated, and the upper bound of the 95% confidence interval for the percentages will be presented. AEs occurring during the infusion and within 1, 24, 48 and 72 hours after the infusion completion will also be summarized.

An adverse reaction will be defined as any AE occurring during the infusion and within 72 hours after the infusion completion OR any AE classed as product-related or with unknown causality.

AEs that occur during an infusion will be summarized by the infusion rate at which the AEs are reported. If necessary, infusion rates will be grouped into different levels.

SAEs and SUSARs will be summarized with all AEs, and separate listings will be provided for SAEs and SUSARs.

All other safety assessments will be summarized descriptively for each treatment group.

Further summaries of AEs will be detailed in the Statistical Analysis Plan.

## 13.4.2. Other Safety Analyses

All other safety assessments will be summarized descriptively.

# 13.5. IgG subclasses and IgG antibodies

The trough levels of IgG subclasses and IgG antibodies against specified antigens will be summarized descriptively for all the Intent-to-Treat (ITT) subjects. This analysis will be conducted for subjects 2 to 5 years of age, 6 to 11 years of age, 12 to 15 years of age, all pediatric subjects (2 to 15 years of age), all adult subjects (aged 16 years and over), then for all subjects.

# 13.6. Pharmacokinetic Analyses

The pharmacokinetics of Subgam-VF will be based on absolute and baseline-adjusted (trough adjusted at steady state) values and will be described using a non-compartmental method. Actual sample times rather than nominal times will be used to calculate pharmacokinetic parameters.

The following PK parameters will be calculated for the Subgam PK population: The maximum observed concentration ( $C_{max}$ ), the time at which  $C_{max}$  was apparent ( $t_{max}$ ), the area under the concentration versus time curve within a dosing interval ( $AUC_{0-\tau}$ ) and the systemic clearance (CL).

Pharmacokinetic variables will be summarized descriptively. This analysis will be conducted for subjects 2 to 5 years of age, 6 to 11 years of age, 12 to 15 years of age, all pediatric subjects (2 to 15 years of age), all adult subjects (aged 16 years and over), then for all subjects.

For the Gammaplex PK population,  $sAUC_{0-\tau}$  will be calculated as the area under the concentration versus time curve within a dosing interval (21 or 28 days), standardized to one week i.e.  $AUC_{0-\tau}$  (21 day)/3 or  $AUC_{0-\tau}$  (28 day)/4. For the Subgam PK population,  $sAUC_{0-\tau}$  is equivalent to  $AUC_{0-\tau}$  (i.e. no standardization required as dosing is weekly).

All PK data collected on all subjects in the Subgam PK population will be listed. The PK population i.e. Subgam PK population combined with the Gammaplex PK population (historical data following administration of Gammaplex 5% IGIV) will be used for the primary and secondary statistical PK analyses.

The trough levels of total IgG will be summarized descriptively for all the subjects in the ITT population. Trough levels in the ITT population will be compared with those from the Gammaplex PK population.

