# 2. LIST OF ABBREVIATIONS AND DEFINITION OF TERMS

AEs Adverse Events

ALT Alanine Transaminase
ANC Absolute Neutrophil Count
Anti-D Anti-D immunoglobulin
AST Aspartate Transaminase
AUC Area under the curve

AUC $_{(0-\tau)}$  Area under the plasma concentration-time curve of the dosing interval Area under the plasma concentration-time curve of the dosing interval

standardized to one week

BMI Body Mass Index

BPL Bio Products Laboratory Limited (Ltd.) (the Sponsor and manufacturer)

BUN Blood Urea Nitrogen
CBC Complete Blood Count
CI Confidence Interval
CL Systemic clearance (PK)

Cmax Maximum concentration in plasma
CFR Code of Federal Regulations
CRO Contract Research Organization

Cryo-Store Archive Facility for Laboratory Samples

CV Coefficient of Variation
DVT Deep Vein Thrombosis
eCRF Electronic Case Report Form
EMA European Medicines Agency

EU European Union

FDA U.S. Food & Drug Administration

HAV Hepatitis A Virus

HBsAg Hepatitis B Surface Antigen

HBV Hepatitis B Virus

HCG Human Chorionic Gonadotropin

HCV Hepatitis C Virus

HIV Human Immunodeficiency Virus

IB Investigator's Brochure

ICH International Conference on Harmonization

IEC Independent Ethics Committee

IgA Immunoglobulin A
IgG Immunoglobulin G

IGIV Immunoglobulin Intravenous

IgM Immunoglobulin M

IMP/IP Investigational Medicinal Product / Investigational Product (EU / US)

IRB Institutional Review Board ITT Intent-To-Treat (population)

IV Intravenous

LDH Lactate Dehydrogenase

Page 7 of 87

MOsmol MilliOsmolae mL Milliliter

NAT Nucleic acid Amplification Test (PCR)

PA Posterior-Anterior

PaO2 Partial pressure of Oxygen in arterial blood

PCR Polymerase Chain Reaction

PID Primary Immunodeficiency Diseases

PK Pharmacokinetic
PVC Polyvinyl Chloride
RNA Ribosenucleic Acid
SAE Serious Adverse Event

SC Subcutaneous SCIG Subcutaneous IgG

SOP Standard Operating Procedure

SUSAR Suspected Unexpected Serious Adverse Reaction

TEAE(s) Treatment-emergent Adverse Event(s)

TEE Thrombo-embolic events

tmax Time to reach the maximum concentration in plasma

UK United Kingdom US United States

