# 4.3. Benefit / Risk Statement

Published data has shown that subcutaneous IgG (SCIG) use in subjects with PID provides protection which is comparable to that found with IGIV therapy.

Infusions of IgGs given subcutaneously (SCIG) were initially used in patients who were unable to tolerate IgG administered either through intravenous (IV) or intramuscular (IM) routes. SCIG has the advantage in that it can be self-administered at a time and location more suitable to the individual and without the need for assistance from a trained professional (other than during the initial training period). This convenience has been associated with an improvement in quality of life.

This form of infusion requires no venous access. Unlike IGIV which is infused directly into the intravascular compartment, SCIG must diffuse first into the lymphatic system and is then Page 17 of 87

subsequently carried into the blood stream via the thoracic duct, therefore with SCIG the intravascular concentration of IgG increases more gradually, peaking at 48-72 hours. The rate IgG enters the circulation appears to be the main driver of systemic tolerability and as such the incidence of systemic adverse events appears to be much lower with SCIG therapy than with IV infusion. Also division of the dose into weekly fractions produces more consistent IgG levels without the peaks and troughs experienced with monthly IGIV infusions. However, with SCIG therapy because some of the IgG is already equilibrating into the extracellular fluid before all of the IgG has entered the bloodstream; and also due to binding and/or degradation of the IgG in subcutaneous tissue, the maximum serum concentration of IgG can be on average 61% of the level achieved with IGIV.

As with any blood product, viral safety is a concern. Subgam-VF undergoes a stringent multistep process, including solvent/detergent treatment, nanofiltration, and a terminal low pH incubation of the finished product, to reduce the risk of potential viral contaminants and enhance the safety of the product.

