# 8.2. Investigational Treatment

# 8.2.1. Dosing Schedule and Rationale

Subgam-VF is a 16% subcutaneous IgG product. The weekly dose of Subgam-VF administered will be calculated by taking the weekly equivalent of the subject's stable IGIV dose, multiplied by 1.37, a dose adjustment coefficient based on other licensed subcutaneous IgG products. If the subject was already receiving a weekly SCIG IgG there will be no dose adjustment. The Subgam-VF dose should remain the same throughout the study, if a subject's weight changes by >5% compared with baseline (screening) or the previous visit, the dose should be adjusted accordingly with the aim of maintaining a stable dose in terms of mg/kg. If the dosage needs to be increased to achieve the required trough IgG level, then this should first be discussed with the CRO Medical Monitor, who will, if needed, discuss with the Sponsor.

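### For the subcutaneous-only Subgam group, the planned systemic clearance can only be apparent clearance (CL/F), and a trough-adjusted version of it would not be a clearance

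*Protocol*

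**What the plan says.** Protocol Section 13.6 gives the parameters for the Subgam PK population as Cmax, tmax, AUC over the dosing interval "and the systemic clearance (CL"), and says that the pharmacokinetics "will be described using a non-compartmental method". Section 11.1 and the synopsis list of PK variables have the same item ("CL– systemic clearance"), and Section 2 expands the abbreviation in the same way ("CL Systemic clearance (PK").

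On the concentrations to be used, Section 11.1 states: "All PK parameters will be calculated based on absolute (uncorrected) and baseline-adjusted (i.e. trough-adjusted at steady state) concentrations". The Pharmacokinetics paragraph of the synopsis and SAP Section 5.4 say the same, and Section 13.6 also names both bases. None of them exempts clearance.

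Subgam-VF is given only by subcutaneous infusion (Sections 7.2 and 8.2.3). The profile covers one weekly interval, with samples before the infusion and 1, 2, 3, 5 and 7 days after it (Table 3). No section mentions apparent clearance or CL/F, gives a bioavailability, or states how clearance is computed. Section 11.1 leaves PK methods to a PK Analysis Plan, and SAP Sections 3 and 14 place the PK analyses there too. That plan is not among the documents.

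**The concern.** There are two separate faults.

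The first is the name. After extravascular dosing, dose divided by steady-state AUC over the interval estimates CL/F. Separating CL from F needs an intravenous profile or an external value of F. The Subgam group has no intravenous profile in this study, and no F is given.

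The second is the trough adjustment. At steady state, the bioavailable dose per interval equals CL times the full AUC over that interval. The trough consists largely of IgG carried over from earlier infusions. Subtracting it removes AUC that belongs in the denominator, and dose divided by what remains is not a clearance.

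The stake is how the tables are read. Clearance is to be summarised for three paediatric bands, all children, adults and all subjects. In a study whose comparator is intravenous, a value labelled systemic clearance invites the reading that IgG from Subgam-VF is eliminated faster. A second table on trough-adjusted data would show values several times larger, with no pharmacokinetic meaning.

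**Working it through.** **Figures available.** The documents state no clearance, F, half-life or weekly peak-to-trough ratio, so there is no clearance figure to reproduce. The dosing interval is 7 days, the sampling days are 0, 1, 2, 3, 5 and 7 (Table 3), and the peak after subcutaneous dosing is put at 48-72 hours (Section 4.3). The dose factor of 1.37 comes with no derivation (Section 8.2.1).

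**Step 1: what dose/AUC estimates.** At steady state F × dose = CL × AUC(0-τ), so dose/AUC(0-τ) = CL/F. Its ratio to CL is 1/F.

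**Step 2: illustration of CL/F against CL.** Suppose 1.37 is exactly 1/F and endogenous IgG is nil.
- F = 1/1.37 = 0.73, and CL/F exceeds CL by 37%.
- The trial re-estimates the factor as 1.37/ratio. At the equivalence limits this is 1.37/1.25 = 1.10 and 1.37/0.80 = 1.71, an excess of 10% to 71%.
- If a share e of the uncorrected AUC is endogenous IgG, dose/AUC relative to CL is 1.37 × (1 − e): 1.23 at 10%, 1.10 at 20%, 1.00 at 27% and 0.82 at 40%. A share near 27% cancels the excess, and a larger one reverses it.

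**Step 3: effect of subtracting the trough.** Let x be the fraction by which the mean level over the week exceeds the trough. The trough-adjusted value is then (1 + x)/x times the absolute one. This is tenfold at x = 0.111 and larger for any smaller x.

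To see what x might be, take a one-compartment model with first-order absorption at steady state, ke = ln 2/half-life:

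C(t) ∝ exp(−ke·t)/(1 − exp(−7ke)) − exp(−ka·t)/(1 − exp(−7ka))

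Half-life and ka are assumptions. Absorption rates of 0.3-0.8/day put the peak at 2.0-2.9 days over all the half-lives below, consistent with 48-72 hours.

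Worked case, half-life 21 days and ka 0.8/day: levels relative to trough on the sampling days are 1.000, 1.103, 1.128, 1.119, 1.065 and 1.000. The trapezoid areas are 1.051 + 1.115 + 1.123 + 2.183 + 2.065 = 7.54. The trough accounts for 7 × 1.000 = 7.00, leaving 0.54, or 7.1% of the AUC. The inflation is 7.54/0.54 = 14.0.

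The same calculation over the range gives these inflation factors:

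| Assumed half-life | ka 0.8/day | ka 0.5/day | ka 0.3/day |
|---|---|---|---|
| 7 days | 4.9 | 6.3 | 9.4 |
| 14 days | 9.4 | 12.4 | 18.6 |
| 21 days | 14.0 | 18.5 | 27.8 |
| 35 days | 23.2 | 30.7 | 46.3 |

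Choosing ka so that the peak falls at 2 to 3 days gives a similar picture: 4.7- to 17-fold at 7 days, 8.8- to 26-fold at 14 days and 13- to 56-fold at 21-35 days.

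**The case against.** **The formula may be elsewhere.** Neither document writes dose/AUC, and the unseen PK Analysis Plan may define CL/F or exempt clearance from the adjustment. This stands as a limit on certainty. But the protocol itself fixes the name and both concentration bases, so it needs correcting even if that plan is sound.

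**The protocol does not say that F is below 1.** A reader might infer this from "also due to binding and/or degradation of the IgG in subcutaneous tissue" in Section 4.3, and take 1.37 as the offset. The documents do not support that. Section 4.3 offers binding and/or degradation, with equilibration into extracellular fluid, as reasons for a lower maximum concentration (61% of the intravenous level on average), not for lower bioavailability. Section 8.2.1 describes the factor only as "multiplied by 1.37, a dose adjustment coefficient based on other licensed subcutaneous IgG products" and gives no mechanism. The 37% is therefore an illustration.

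**Trough adjustment could be defended as removing endogenous IgG.** Eligible diagnoses are mixed, and some subjects may make IgG. Uncorrected dose/AUC is then not exactly CL/F either, which belongs in the fix. But a steady-state trough also holds accumulated product, so subtracting it does not isolate the endogenous part.

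**Nothing depends on clearance.** This stands. The primary, secondary and dose-refinement analyses in Sections 13.6.1 and 13.6.2 use AUC or sAUC. Section 13.6 derives only sAUC for the Gammaplex group, so it plans no comparison of clearance between products. A reader might also fear for the schedule modelling in Section 13.6.3, but that section does not name non-compartmental clearance as an input. Its example compares two regimens of the same product, for which CL/F is the relevant quantity.

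**Conclusion.** The point holds as a minor correction. The name is wrong for the Subgam PK population whatever the value of F, given the usual non-compartmental formula. A trough-adjusted dose/AUC at steady state is not a clearance whatever the half-life.

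Only the sizes are conditional. The 5- to 19-fold and 14- to 46-fold inflation ranges rest on a one-compartment model and on half-lives that the documents do not give. A flat statement that the error is an order of magnitude would go too far: at 7 days it is about 5- to 9-fold for the absorption rates used. The difference between CL/F and CL rests on reading 1.37 as 1/F for this product and on the endogenous share of AUC, and could be positive, nil or negative for uncorrected data.

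The effect is confined to descriptive tables and how they are read.

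**What to change.** 1. For the Subgam PK population, in the synopsis list of PK variables and in Protocol Sections 11.1 and 13.6, replace systemic clearance (CL) with apparent clearance, CL/F = weekly dose / AUC(0-τ) from absolute concentrations. Add CL/F to Section 2.
2. Note beside the definition that uncorrected total IgG includes any endogenous IgG, so the value is CL/F only to the extent that this is small.
3. Exclude clearance from the parameters calculated on trough-adjusted concentrations in the synopsis, Protocol Sections 11.1 and 13.6, SAP Section 5.4 and the PK Analysis Plan.
4. Do not relabel throughout. The synopsis and Section 11.1 list CL for the PK population, which by Section 13.2.2 includes the intravenous Gammaplex subjects, whereas Section 13.6 lists it for the Subgam group only. State which is meant, and keep CL for Gammaplex data if it is calculated there.
5. State that CL/F is not to be read against an intravenous CL as a difference in elimination.

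The cost is wording in the protocol, the SAP and the PK Analysis Plan, and the loss of one uninterpretable table. Sampling, data and the primary and secondary analyses are unchanged.
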